8.11 Leukapheresis

On rare occasions, an allergic reaction to the citrate used during leukapheresis will require that the procedure be stopped early. Symptoms should be treated according to the site's standard practice.

8.12 Gut Biopsy

On extremely rare occasions, the gut biopsy via flexible sigmoidoscopy may cause pain, infection, bleeding, or perforation of the intestinal tract. If such a complication occurs, the participant will have appropriate clinical management in conjunction with the participant's health care provider.

9.0 CRITERIA FOR DISCONTINUATION

9.1 Premature Study Drug Discontinuation

- Drug-related toxicity ([section 8.1](#))
- Requirement for prohibited concomitant medications ([section 5.4](#))
- Pregnancy and/or breastfeeding
- Request by participant to discontinue treatment
- Clinical reasons believed life-threatening by the physician, even if not addressed in the [toxicity section](#) of the protocol

9.2 Premature Study Discontinuation

- Never started ART
- Started ART after 48 hours after enrollment and determined by the protocol team to be ineligible for continued participation
- Does not have HIV-1 infection
- **Participant confirmed to be Fiebig VI will discontinue after week 24 in Step 1.**
- Failure by the participant to attend three consecutive study visits
- Participant has **confirmed** VF as defined in [section 6.3.4](#)
- **In Step 1, interrupted ART ≥ 7 consecutive days and has not previously demonstrated an HIV-1 RNA < 50 copies/mL (prior to the interruption lasting ≥ 7 consecutive days)**
- Request by the participant to withdraw, **including withdrawal to enable participation in another study.**
- Request of the primary care provider if s/he thinks the study is no longer in the best interest of the participant.
- Participant judged by the investigator to be at significant risk of failing to comply with the provisions of the protocol as to cause harm to self or seriously interfere with the validity of the study results.
- At the discretion of the IRB/EC, NIAID, Office for Human Research Protections (OHRP), other government agencies as part of their duties, investigator, or industry supporter.

10.0 STATISTICAL CONSIDERATIONS

10.1 General Design Issues

This is a prospective, open-label study to measure the effects of early ART on the establishment of HIV-1 reservoir and HIV-1-specific immunity. Participants with AHI will have an enrollment visit and initiate ART at the time of enrollment. Each participant will be followed **on study** for up to **216 weeks (72 weeks on Step 1 and 144 weeks on Step 2)** unless they are Fiebig VI at ART initiation in which case their last visit will be **no later than week 24 on Step 1**. The primary endpoint is CAHD in 5 million blood-derived CD4+ T-cells assayed by qPCR at week 48 **on Step 1**. Only participants who have not met criteria for permanent study discontinuation, have not missed more than 6

consecutive days of ART and have HIV-1 RNA <50 copies/mL at week 48 **on Step 1 will be included in the primary efficacy analysis**. If adequate sample and analyzable data are not available from the week 48 visit, week 49 will be used instead.

Characterization of Fiebig stage using samples at the time of ART initiation will be performed with results known within 12 weeks based on standardized, centralized testing; this will define the analysis groups. **Each study group had a target enrollment of 50 participants under protocol Version 1.0. Study Groups 2 and 3 have reached their target enrollment and therefore the original inclusion criteria from protocol Version 1.0 corresponding to these groups are no longer applicable for eligibility into the study.** Because Fiebig stage for the analysis comparison will not be known until after therapy is initiated, over-enrollment based on available data at the time of entry may be implemented.

10.2 Outcome Measures

10.2.1 Primary Outcome Measures

10.2.1.1 CAHD per 5 million CD4+ T-cells at week 48 **on Step 1**

10.2.2 Secondary Outcome Measures

10.2.2.1 HIV-1-specific CD4+ and CD8+ T-cell responses to nef/tat/rev/vpr/vpu, gag, pol and env by flow cytometry prior to ART initiation and while HIV-1 RNA is suppressed on ART

10.2.2.2 Cell-associated HIV-1 RNA per 5 million CD4+ T-cells prior to ART initiation and while HIV-1 RNA is suppressed on ART

10.2.2.3 Cell-associated HIV-1 RNA/DNA ratio in participants with detectable CAHD prior to ART initiation and while HIV-1 RNA is suppressed on ART

10.2.3 **Other** Outcome Measures

10.2.3.1 Frequency of non-transmitted epitope escape mutants prior to ART initiation and week 48 **on Step 1**

10.2.3.2 CAHD, HIV-1-specific immune responses and single copy HIV-1 RNA in blood; CAHD in gut; and CAHD and single copy HIV-1 RNA in CSF at any time **on Step 1** from week 60 to week 72 in participants who **consent and** undergo the optional procedures and have available data

10.2.3.3 Innate immune responses such as NK cells, ADCC, and ADCP prior to ART initiation and while HIV-1 RNA is suppressed on ART

- 10.2.3.4 Different HIV-1 molecular forms (unintegrated HIV-1 DNA, integrated HIV-1 DNA, total HIV-1 DNA) in participants with detectable CAHD prior to ART initiation and while HIV-1 RNA is suppressed on ART
- 10.2.3.5 Genetic factors such as HLA typing and CCR5 delta-32 genotyping, including relationships with virologic and immunologic outcomes prior to ART initiation and while HIV-1 RNA is suppressed on ART
- 10.2.3.6 Integration sites prior to ART initiation and while HIV-1 RNA is suppressed on ART

10.3 Randomization and Stratification

There is no randomization or stratification.

10.4 Sample Size and Accrual

The primary study objective is to compare the primary outcome measure at week 48 **on Step 1** after ART dichotomized as: 0 versus >0 copies of CAHD in 5 million blood-derived CD4+ T-cells. The groups are expected to differ in likelihood that a participant has no detectable total HIV-1 DNA, with percentages estimated to be:

Fiebig I/II: 75%
Fiebig III/IV: 25%
Fiebig V: <5%

Forty-two (42) virologically suppressed participants at week 48 **on Step 1** per group will provide high power to detect differences between all three groups based on this primary endpoint: >95% power for Fiebig I/II versus III/IV, >95% power Fiebig I/II versus V and 80% power for Fiebig III/IV versus V (assuming 3.5% for Fiebig V participants), based on Fisher's exact test with type I error rate of 0.05 for each pairwise comparison. Table **10.4-1** below shows power for the comparison between Fiebig I/II versus III/IV with different underlying probability of undetectable cell-associated HIV-1 DNA at week 48 with 42 participants per group. The study will have moderate power (76%) to detect a difference between the two groups even with higher estimated probability in Fiebig III/IV group (35%) and lower estimated probability in Fiebig I/II group (65%).

Table **10.4-1**: Power Comparisons

Fiebig I/II	Fiebig III/IV		
	25%	30%	35%
75%	>95%	>95%	95%
70%	>95%	95%	88%
65%	95%	88%	76%

It is further assumed that 90% of participants who initiate study treatment will remain HIV-1 RNA <50 copies at week 48 for primary endpoint evaluation. Taking into account a

15% lost to follow-up rate and insufficient samples at primary outcome week, the total sample size is **196 (a target enrollment of 50 per group)**.

NOTE: Groups 2 and 3 closed to enrollment under protocol Version 1.0.

The sample size increase to 196 participants is intended to aid in meeting the accrual target for Group 1 and increase the number of early-treated participants engaged in the cohort that are potentially eligible for future studies. This is an estimation of the additional number of participants that will need to be enrolled in order to fully accrue Group 1 (since group assignment is unknown at the time of enrollment), based on the current rate of participants who were estimated to be in Group 1, and determined to be in Group 1 at study entry after centralized testing.

Based on the available Fiebig staging data as of May 15, 2019, after the completion of centralized testing, 31% of participants estimated to be in Group 1 were determined to be in Group 1, while 50% were determined to be in Group 2. Group 1 has enrolled 37 participants. Group 2 had enrolled 63 participants, and Group 3 had enrolled 54 participants. Assessing the current group counts and rates, we anticipate that, with 196 participants enrolled (an additional 36 enrollments after replacing Fiebig VI and HIV negative participants), approximately 50 participants will be determined to be in Group 1.

Secondary objectives are largely exploratory without formal sample size calculation. However, based on data from the RV254 study, HIV-1-specific CD4+ T-cell responses to gag after ART are expected to be 15% in Fiebig I/II versus 30% in Fiebig III/IV versus 80% in Fiebig V which will provide 30% power for Fiebig I/II versus III/IV, >90% power for Fiebig V versus the other two groups.

It is anticipated that the study will take **36 months to accrue** with one third of the participants accrued during the first 6 months after at least three international sites have enrolled at least one participant.

10.5 **Data and Safety** Monitoring

Accrual, baseline characteristics (including baseline laboratory values), conduct of the study (including premature study discontinuations, data availability and sample acquisition), any ART interruptions, VFs, and all reported toxicities and AEs will be monitored by the team during the study. The team will also closely monitor the Fiebig stages of the study population as defined by the standardized testing of samples obtained at ART initiation. In addition, the study will be reviewed by a Study Monitoring Committee (SMC) according to ACTG standard operating procedures. The SMC will review accrual, baseline characteristics (including baseline laboratory values), Fiebig stage at ART initiation, AE summaries, CD4+ T-cell counts and HIV-1 RNA levels/suppression over time, study and ART discontinuations (and reasons), and completeness of follow-up and sample availability. The SMC will convene, at a minimum, 6 months after the first participant is enrolled or after 25 participants are enrolled, whichever is earlier and approximately annually thereafter or at the request of the SMC.

Furthermore, the CMC or the team may, at any time it thinks appropriate, ask for the SMC to independently review all available safety data.

Since characterization of Fiebig stage using samples at the time of ART initiation will be performed with results known within 12 weeks based on standardized, centralized testing, an estimated Fiebig group at enrollment based on inclusion criteria from [section 4.1.1](#), as shown in the table below will provide additional real-time monitoring for accruals into each study group. Each Fiebig stage from I through IV has a median duration of approximately 5 days, the Fiebig stage at 7 days prior to enrollment may be expected to advance by one or possibly two stages by the time of enrollment. Both Fiebig stage determinations (centralized tested or estimated by inclusion criteria) will be used to guide accrual once enrollment is completed in at least one Fiebig group. For instance, **Groups 2 and 3 have reached their enrollment target under protocol Version 1.0, thus enrollment is closed for those two groups.**

Table 10.5-1. Expected Fiebig Group Based on Inclusion Criteria ([section 4.1.1](#))

Inclusion Criteria #	Inclusion Criteria Details	Expected Fiebig Group
a	A detectable HIV-1 RNA obtained within 28 days prior to study entry AND a non-reactive HIV-1 antibody within 7 days prior to entry	Group 1 (Fiebig I-II)
b	ARCHITECT or GSCOMBO S/CO ≥ 10 within 7 days prior to entry AND a non-reactive HIV-1 antibody within 7 days prior to entry	Group 1 (Fiebig I-II)
c	ARCHITECT or GSCOMBO S/CO ≥ 1 within 7 days prior to entry AND a non-reactive HIV-1 antibody within 7 days prior to entry AND a known prior S/CO < 0.5 within 90 days prior to entry	Group 1 (Fiebig I-II)
d	ARCHITECT or GSCOMBO S/CO > 0.5 but < 10 within 7 days prior to entry AND a non-reactive HIV-1 antibody within 7 days prior to entry AND detectable HIV-1 RNA within 7 days prior to entry	Group 1 (Fiebig I-II)

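### Protocol section 10.4 states 80% power for Fiebig III/IV versus V at 42 per group; the Fisher test that matches its other printed powers gives 77.9%

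*Protocol*

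**What the plan says.** Protocol section 10.4 bases the primary comparison on the proportion of participants with no detectable cell-associated HIV-1 DNA at week 48. The expected proportions are 75% for Fiebig I/II, 25% for Fiebig III/IV and under 5% for Fiebig V. The sample size per group is given as "Forty-two (42) virologically suppressed participants at week 48". The test is Fisher's exact test with a type I error of 0.05 for each pairwise comparison; sidedness is not stated.

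Three headline powers follow: above 95% for I/II versus III/IV, above 95% for I/II versus V, and "80% power for Fiebig III/IV versus V (assuming 3.5% for Fiebig V participants"). Table 10.4-1 gives nine further powers for I/II versus III/IV, down to 76% for 65% versus 35%. For a secondary T-cell response expected at 15% versus 30%, the section adds a figure, "which will provide 30% power for Fiebig I/II versus III/IV".

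On enrolment, the section assumes that "90% of participants who initiate study treatment will remain HIV-1 RNA <50 copies at week 48 for primary endpoint evaluation". It then allows for a "15% lost to follow-up rate and insufficient samples at primary outcome week, the total sample size is" 196, with a target of 50 per group. For the staging data of May 15, 2019 it reports that "Group 2 had enrolled 63 participants, and Group 3 had enrolled 54 participants". SAP section 2.8 gives no calculation of its own and refers back to protocol section 10.4.

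**The concern.** The III/IV versus V power is one of three headline figures for the primary pairwise comparisons, and the only one close to the conventional 80% line. All its inputs except sidedness are printed, so it can be recomputed. If the named test falls short of 80% while reproducing the neighbouring figures, the printed value is wrong as it stands. A reader would then take 42 per group to be just enough for this comparison when it is slightly too few.

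**Working it through.** **Inputs, all from protocol section 10.4:** n = 42 per group; p = 0.25 for Fiebig III/IV and 0.035 for Fiebig V; Fisher's exact test; alpha 0.05 per comparison. Two-sided testing is an assumption, checked in step 1.

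**Formula.** Power = Σₓ Σᵧ Bin(x; n₁, p₁) · Bin(y; n₂, p₂) · I[Fisher p(x, y) ≤ 0.05], summed over every possible pair of counts.

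**Step 1. Reproduce the section's other figures (two-sided, 42 per group).**

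| Comparison | Computed | Printed |
|---|---|---|
| 65% v 35% | 76.26 | 76 |
| 70% v 35%; 65% v 30% | 88.64 | 88 |
| 70% v 30% | 95.65 | 95 |
| 75% v 35%; 65% v 25% | 95.75 | 95 |
| 75% v 30%; 70% v 25% | 98.74 | >95 |
| 75% v 25% | 99.73 | >95 |
| 75% v 3.5% | about 100 | >95 |
| 15% v 30% (secondary; 42 per group assumed) | 30.05 | 30 |

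The table entries match if decimals were cut off rather than rounded. One-sided Fisher at 0.05 does not fit: it gives 82.6 where 76 is printed and 39.8 where 30 is printed. Two-sided testing is therefore the reading that the section's own numbers support.

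**Step 2. Apply the same test to III/IV versus V.** For 25% versus 3.5% at 42 per group the power is **77.92%**, against the stated 80%: 80 − 77.92 = 2.08 points. Defining the two-sided p-value as twice the one-sided value also gives 77.92%.

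**Step 3. What would give 80%?**

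- More participants: 78.80% at 43 per group and 80.11% at 44.
- A lower Fiebig V rate at 42 per group: 79.83% at 3.2% and 80.46% at 3.1%.
- Another method: one-sided Fisher gives 85.8%. The uncorrected normal approximation gives 81.7%, but 79.6% where the table prints 76%. The continuity-corrected normal approximation gives 71.7%. Mid-p gives 80.85% or 82.59%, depending on how tied tables are treated, but then 32.7% or 35.6% where the section prints 30%.

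**Step 4. Does it matter at the enrolled sizes?** Groups 2 and 3 had 63 and 54 participants. The power is shown for each way of reading the two stated losses (10% not suppressed; 15% lost or without adequate sample), with evaluable numbers rounded down.

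| Reading of the losses | Group 2 | Group 3 | Power, 25% v 3.5% |
|---|---|---|---|
| No overlap | 63 × 0.75 = 47.25, so 47 | 54 × 0.75 = 40.5, so 40 | 82.4% |
| Independent | 63 × 0.90 × 0.85 = 48.2, so 48 | 54 × 0.90 × 0.85 = 41.3, so 41 | 83.3% |
| 15% covers all loss | 63 × 0.85 = 53.55, so 53 | 54 × 0.85 = 45.9, so 45 | 87.7% |

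Every reading exceeds the 80% that the section states.

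**The case against.** **The gap is small, and the input behind it is soft.** It is about two points, and Fiebig V is listed only as under 5%; a rate near 3.1% would give 80%. Rounding 78 up to 80 cannot be strictly excluded either. This stands as an argument about importance. But the section attaches its 80% to a rate of 3.5%, and the other specific powers are printed to the whole percent. Cutting off decimals would give 77 and ordinary rounding 78.

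**The calibration is imperfect.** The table matches only by truncation. The 30% secondary figure is printed without a sample size or test, in a paragraph that disclaims formal sample size calculation. One mid-p variant fits the table as well as Fisher does, and is ruled out only by that 30%. This is fair, and it limits how much weight the 30% can carry. Mid-p is still not the test that the protocol names, and the named test gives 77.9%.

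**A stronger reading is tempting: that the target of 50 is too low.** A reader might infer that the 10% and the 15% must both be removed, leaving 50 × 0.90 × 0.85 = 38.25 evaluable (37.5 if the losses do not overlap) instead of 42. The documents do not support calling this an error. The 90% is stated among all who start treatment, so people lost to follow-up may already be within the 10%. If the 15% covers all loss, 42 / 0.85 = 49.4, which gives the stated 50. Multiplying the losses would require 42 / 0.765 = 54.9, and adding them 42 / 0.75 = 56; neither is the plan's target. The wording is terse, but the target is not shown to be wrong.

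**Conclusion.** The stated 80% is wrong as written. With the section's own inputs and the two-sided Fisher test, the power for III/IV versus V at 42 per group is 77.9%. The conclusion rests on two-sided testing, which the protocol does not state but which its other printed powers support.

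The consequence is minor. A reader should not infer that the study is underpowered for this comparison: at the sizes already enrolled, the power is about 82% to 88%. Those figures take no account of the exclusion for ART interruption of 7 or more days, for which section 10.4 gives no rate. The claims above 95% for the other two primary comparisons are unaffected, and no decision on enrolment, endpoint or analysis depends on the correction.

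**What to change.** In protocol section 10.4, restate the power for Fiebig III/IV versus V as about 78% at 42 per group, and say that the test is two-sided. SAP section 2.8 needs no edit because it only points there.

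Optionally, add one sentence confirming that the 15% includes participants not suppressed at week 48, if that was the intention; it is the reading that gives 50 per group.

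The cost is one figure and a few words. No powers need to be recalculated from accrued group sizes, and no extra enrolment is needed.

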10.6 Analyses

Analysis of the primary **efficacy** will be restricted to participants who maintain HIV-1 RNA < 50 copies/mL at week 48 **on Step 1** with no ART interruption of ≥ 7 consecutive days and have available CAHD results **from** week 48 or week 49. Specifically, plasma HIV-1 RNA by commercial assay must be < 50 copies/mL at week 48 with no prior VF ([section 6.3.4](#)). This study is designed to evaluate the effect of suppressive ART initiated in different stages of AH1 on the establishment and persistence of HIV-1 reservoirs; this is the rationale for analyzing HIV-1 DNA only among virally suppressed participants and not in those with incompletely suppressed viremia (> 50 copies/ml). Primary outcome measures will be summarized as a binary outcome, 0 copies versus > 0 copies of CAHD per 5 million CD4+ T-cells **assessed separately and jointly by gag- and integrase-assays. Each participant's primary endpoint sample will be tested twice by gag-**

and integrase-assays. For the primary outcome measure, in order for a participant to be considered as having 0 copies of CAHD, the participant must be found to have an undetectable CAHD result from both assays. Proportion of 0 copies of CAHD will be compared pairwise between groups using Fisher's exact test. 95% confidence interval for the proportion estimated will be calculated using the exact binomial distribution. The analysis groups will be Fiebig I/II, Fiebig III/IV, and Fiebig V, as defined by the standardized testing of samples at ART initiation. **Supplemental analyses** will use Wilcoxon rank sum test to compare the primary outcome measure on the continuous scale between analysis groups, **separately for the results from the gag- and integrase assays.** We will also examine the primary outcome measures that include participants with extended periods of ART interruption (≥ 7 consecutive days) while maintained HIV-1 RNA < 50 copies/mL at week 48. For clades with sufficient data, supplemental sensitivity analyses will compare Fiebig stages stratified by HIV subtype.

Study and study treatment discontinuations (and reasons) will be summarized. In addition, use of non-study-provided ART will be summarized including reasons (if any) for participants to change from study-provided ARV regimen to non-study-provided ARV regimen.

Analysis of secondary outcome measures will use the same approach as for the primary outcome measure if the outcome is binary. Wilcoxon rank-sum tests will be used to compare the continuous secondary outcome measures between groups. Rank-based Spearman correlations will describe association between outcome measures.

11.0 PHARMACOLOGY PLAN

Not applicable.

12.0 DATA COLLECTION AND MONITORING

12.1 Records to Be Kept

eCRFs will be made available to sites for data entry. Participants must not be identified by name on any data submitted to the DMC. Participants will be identified by the patient identification number (PID) and study identification number (SID) provided by the ACTG DMC upon registration.

12.2 Role of Data Management

12.2.1 Instructions concerning entering study data on eCRFs will be provided by the ACTG DMC. Each CRS is responsible for keying the data in a timely fashion.

12.2.2 It is the responsibility of the ACTG DMC to assure the quality of computerized data for each ACTG study. This role extends from protocol development to generation of the final study databases.

12.3 Clinical Site Monitoring and Record Availability

12.3.1 Site monitors under contract to the NIAID will visit participating clinical research sites to review the individual participant records, including consent forms, eCRFs, supporting data, laboratory specimen records, and medical records (physicians' progress notes, nurses' notes, individuals' hospital charts), to ensure protection of study participants, compliance with the protocol, and accuracy and completeness of records. The monitors also will inspect sites' regulatory files to ensure that regulatory requirements are being followed and sites' pharmacies to review product storage and management.

12.3.2 The site investigator will make study documents (e.g., consent forms, drug distribution forms, eCRFs), and pertinent hospital or clinic records readily available for inspection by the **ACTG**, local IRB/EC, the site monitors, the NIAID, the OHRP, **the industry supporter or designee, other local, US, and international regulatory entities** for confirmation of the study data.

